5.3.6 Number of Participants

72 participants (36 at each study site) were enrolled in CI02 with a goal of at least 60 completing the efficacy evaluation (first 11 weeks and 6 study visits) and at least 30 completing the long-term safety evaluation. Based on our drop-out rate analysis (see Section 8.4), we calculate that continuation of at least 42 participants to the long-term safety evaluation will ensure that 30 will complete the entire study. All participants will be automatically selected to participate in the long-term safety portion of the investigation.

To ensure that 60 participants successfully complete the study (and that 30 participants successfully complete the long-term safety study), it will still be possible to enroll participants to replace drop-outs at any point during the study until 60/30 participants have successfully completed the study, provided that the crossover study blind has not yet been broken (although active recruitment may discontinue when the estimated enrollment is met as described above). Note that if additional sites are used, the requirement for the minimum number of patients at each site will be modified accordingly.

5.3.7 Estimated Time Needed to Enroll Participants

Between both study sites, we expect approximately 3 to 6 patients to be enrolled per week. Since 60 to 69 participants need to be enrolled, the time to complete enrollment is conservatively estimated at 10 to 23 weeks from the time of initiation of the investigation at the last site.

5.3.8 Total Study Duration

The clinical investigation will continue until at least 60 participants have successfully enrolled in and completed the efficacy portion of the study and at least 30 participants have successfully enrolled and completed the long-term safety evaluation. This is expected to occur between 8 and 11 months (35 and 48 weeks) from initiation of the investigation, assuming the last patient enrolled is randomly assigned to complete the safety study.

5.3.9 Procedures for the Replacement of Participants

As described above, additional participants will be enrolled to account for the maximum expected drop-out rate to ensure that at least 60 participants complete the efficacy portion of the study and at least 30 participants complete the safety portion of the study.

J3 Bioscience, Inc.	Clinical Investigation Plan and Protocol CI02	CI02-CIP Rev. 08 Page 33 of 75
	A Pivotal Clinical Investigation to Evaluate the Safety and Efficacy of J3 Bioscience Lubricating Intravaginal Ring VR101 in Relieving Symptoms of Vaginal Dryness	

The handling of data from participants who do not complete the study is described in Sections 8.8 and 8.9.

VR101 safety data (recording and analyses of adverse events) will be included in the assessment of safety endpoints regardless of how long a participant remains in the study.

5.4 Procedures

5.4.1 Participant Screening

- Each work day, the schedule of any clinic associated with one of the facilities participating in the clinical investigation may be screened for patients who may meet the eligibility criteria. Potential participants' names will be communicated to the appropriate study staff who may contact them to determine their interest in participating in the study.
- Interested clinicians and nurses will notify staff of participating clinics of potential participants.
- Participant also may be recruited from clinics or by word of mouth, or in response to ads placed to inform the public of the opportunity to participate in the study.
- The study will be listed on the ClinicalTrials.gov website, which could also attract participants.

5.4.2 Participant Enrollment/Recruitment

- Interested women will be invited to learn more about this study. The clinical staff initially may meet and present the study to patients during their planned clinic visits. If an interested possible participant calls the study coordinator, the potential participant may be given information over the phone and emailed (or mailed) the informed consent form for review.
- The study information will be presented to potential participants and explained. Study Visit #1 will be scheduled if interest persists and the potential participant meets inclusion/exclusion criteria (all except for the baseline VHI assessment, which will be performed immediately prior to placement of the first ring). Staff may email the informed consent form (ICF) to the potential investigation participant for review before her scheduled visit.
- A signed copy of the informed consent form (ICF) will be provided to the participant.
- The ICF will be stored with the participant's record or as part of the required investigation documentation.

NOTE: Directions to study center locations and parking will be provided as necessary.

J3 Bioscience, Inc.	Clinical Investigation Plan and Protocol CI02	CI02-CIP Rev. 08 Page 34 of 75
	A Pivotal Clinical Investigation to Evaluate the Safety and Efficacy of J3 Bioscience Lubricating Intravaginal Ring VR101 in Relieving Symptoms of Vaginal Dryness	

5.4.3 Visit Schedule and Description

Participants must return to the clinic for determination of VHI Scores on the schedule shown in Tables 4 and 5.

NOTE: In order to minimize scoring inconsistencies, each participant's VHI Score will be assessed by the same clinician each time her VHI is assessed, meaning that if a clinician is to complete the Visit 1 (baseline) assessment for a participant, the same clinician should be available for all subsequent exams that are part of the efficacy portion of the study (approximately 7, 28, 49, 56, and 77 days later). If this is not possible, deviations are acceptable, provided that measurements that affect the Primary Efficacy Hypothesis (Visits 1, 3, 4 and 6) are measured by the same clinician for a given participant.

NOTE: Participants will be instructed to refrain from vaginal intercourse 24 hours prior to each scheduled visit. If the participant reports to having vaginal intercourse in this time-period, she will be rescheduled for the next clinic day if possible.

NOTE: The "EOT" visit and "Final PC" described in Table 4 are copied from a previous Protocol revision and are not needed for participants completing the investigation per protocol. However, the EOT visit and Final PC may be used for participants who drop from the study in between scheduled Visits.

Table 4. Schedule of Events (GROUP V1S2, V – VR101, S – Sham Control)

Visit	1	2	PC ¹	PC	3	PC	4	5	PC	PC	6	PC	PC	PC	7	PC	8	PC	9	PC	EOT ²	Final PC ⁵
Day (Nominal)	0	7	14	21	28	35	49	56	63	70	77	84	91	98	105	112 119 126 133	140	147 154 161	168	175	Study Withdrawal 4	7 Days Post Removal
Informed Consent	X																					
Assign Subject Number	X																					
I/E Criteria	X																					
Demographics	X																					
Height & Weight	X																					
Concomitant Therapy	X	X			X		X	X			X					X		X		X	X	
Contraception	X																					
Pregnancy Test	X				X		X				X					X		X		X	X	
Pre-Study Survey	X					X																
Medical History	X																					
Pre-Procedure Survey		X			X		X	X			X					X		X		X		
VHI Assessment	X ⁶	X			X ⁶		X ⁶	X			X ⁶					X		X		X	X	
pH Assessment	X	X			X		X	X			X					X		X		X		
Post – Removal Survey		X			X			X			X					X		X		X		
Randomization	X																					
Device Dispensing		X			X		X	X			X					X		X				
Device Insertion	V	V	V	V			S	S	S	S	V	V	V	V	V	V	V	V	V	V		
Post-Insertion Survey	X	X					X	X			X					X		X				
Adverse Events	X	X			X		X	X			X					X		X		X	X	
Diary Dispensing	X	X			X		X	X			X					X						
End of Use Survey					X						X								X			
Phone Call Survey			X	X		X			X	X									X		X	
Phone Call Ring Insertion Reminder			X	X					X	X		X	X	X		X						
Returned Ring Collection ³		X ³			X ³		X ³	X ³			X ³					X ³		X ³		X ³	X ³	
Diary Collection/Compliance		X			X		X	X			X											

¹ PC= Phone Call² EOT= End of Treatment, whether premature or after completion of the investigation.³ The subject will return all rings that were expelled or were removed prior to the 5-7 days of use and could not be reinserted for any reason. See Section 5.4.3⁴ May be used for any study participants (V1S2 or S1V2) who withdraw from the study between scheduled Visits⁵ If the “EOT” visit occurs within 7 ± 2 days of final ring removal, the “Phone Call Survey” can be administered in person and an additional follow-up call is not needed

⁶ The same PI/Sub-I needs to complete the VHI at least on Visits 1, 3, 4 and 6 if at all possible. See Section 5.4.3

Table 5. Schedule of Events (GROUP S1V2, S – Sham Control, V – VR101)

Visit	1	2	PC	PC	3	PC	4	5	PC	PC	6	PC	7	PC	8	PC	EOT ²	Final PC ⁴
Day (Nominal)	0	7	14	21	28	35	49	56	63	70	77	84 91 98	105	112 119 126 133	140	147	Study Withdrawal 3	7 Days Post VR101 Removal
Informed Consent	X																	
Assign Screening Number	X																	
I/E Criteria	X																	
Demographics	X																	
Height & Weight	X																	
Concomitant Therapy	X	X			X		X	X			X		X		X		X	
Contraception	X																	
Pregnancy Test	X				X		X				X		X		X		X	
Pre-Study Survey	X																	
Medical History	X																	
Pre-Procedure Survey		X			X		X	X			X		X		X			
VHI Assessment	X ¹	X			X ¹		X ¹	X			X ¹		X		X		X	
pH Assessment	X	X			X		X	X			X		X		X			
Post-Removal Survey		X			X			X			X		X		X			
Randomization	X																	
Device Dispensing		X					X	X			X		X					
New Device Insertion	S	S	S	S			V	V	V	V	V	V	V	V	V			
Post-Insertion Survey	X	X					X	X			X		X					
Adverse Events	X	X			X		X	X			X		X		X		X	
Diary Dispensing	X	X					X	X			X		X					
End of Use Survey					X						X				X			
Phone Call Survey			X	X		X			X	X					X		X	
Phone Call Ring Insertion Reminder			X	X					X	X		X		X				
Returned Ring Collection ²		X			X		X	X			X		X		X		X	
Diary Collection/Compliance		X			X		X			X								

¹The same PI/Sub-I needs to complete the VHI at least on Visits 1, 3, 4 and 6 if at all possible. See Section 5.4.3

² The subject will return all rings that were expelled or were removed prior to the 5-7 days of use and could not be reinserted for any reason. See Section 5.4.3

³ May be used for any study participants (V1S2 or S1V2) who withdraw from the study between scheduled Visits

⁴ If the “EOT” visit occurs within 7 ± 2 days of final ring removal, the “Phone Call Survey” can be administered in person and an additional follow-up call is not needed

Follow-up phone calls will be conducted weekly in some weeks where the participant does not return to the clinic (days 14, 21, 63 and 70). Follow-up phone calls will also be conducted on day 35 and 147 (if applicable). The follow-up phone calls will be used to ask survey questions regarding their experience with the ring, as well as to remind participants of their responsibilities per their signed ICFs.

On days 84, 91, 98, 112, 119, 126, 133, 147, 154 and 168 no survey data will be collected, but participants will be given a reminder by phone to remove the VR101 and insert a new one.

J3 Bioscience, Inc.	Clinical Investigation Plan and Protocol CI02	CI02-CIP Rev. 08 Page 38 of 75
	A Pivotal Clinical Investigation to Evaluate the Safety and Efficacy of J3 Bioscience Lubricating Intravaginal Ring VR101 in Relieving Symptoms of Vaginal Dryness	

Visit 1/4 - First Ring Insertion

NOTE: If this is a participant's first visit, the baseline VHI assessment and IVR placement must occur on the same day. If the baseline VHI assessment and first IVR placement attempt does not occur within 30 days of initial screening procedures, determination of participant's eligibility must be re-reviewed. Participants will be asked to complete a Pre-Study survey that will gather general demographic information as well as ask questions about vaginal dryness and the effects on sexual activity.

1. Assign a unique screening identifier to each participant (different from the Participant Number) and complete initial screening procedures.
2. Participants will complete a Pre-Study Survey (Visit 1) or a Pre-Procedure Survey (Visit 4).
3. Participants will be asked to provide a urine sample for a pregnancy test.
4. Participants will undergo a brief vaginal health assessment which will include a pH test and assignment of VHI scores (see Table 6). During Visit 1, if a participant is assigned a VHI score of 22 or lower (and met all other inclusion/exclusion criteria), she will be enrolled in the study and randomized. The participant will be assigned the next available (lowest remaining) Participant Number.
5. Enrolled participants will be provided with a package of either at least 6 each VR101 devices or at least 6 each sham controls (one for each of the first 4 weeks and at least 2 spares) with printed instructions for use. During Visit 1, the Participant will be given a package containing the Participant Number followed by the letter "A" (for example Participant 1 will be given a package labeled "1A"). During Visit 4, the Participant will be given a package containing the Participant Number followed by the letter "B" (for example Participant 1 will be given a package labeled "1B"). Participant numbers will be pre-randomized by the Sponsor, and only the Sponsor will have access to the randomization schedule. No additional information, verbal or otherwise, will be provided by the clinician to participants on the use of the device.
6. Enrolled participants will be shown to a private clinic area or restroom to self-insert one of the devices from package "A" (Visit 1) or "B" (Visit 4).
7. After insertion, participants will be asked to complete a Post-Insertion Survey that queries their first impressions of the IVR and the insertion process. If a participant has difficulty with placement, she can choose to not place the ring and will be withdrawn from the study. The first ring will remain in the vagina for 7 ± 2 days.
8. Participants will be given a daily diary to complete and return to study staff at each subsequent study visit. The diary will request information on comfort of device use during daily activities and symptoms of vaginal dryness.

J3 Bioscience, Inc.	Clinical Investigation Plan and Protocol CI02	CI02-CIP Rev. 08 Page 39 of 75
	A Pivotal Clinical Investigation to Evaluate the Safety and Efficacy of J3 Bioscience Lubricating Intravaginal Ring VR101 in Relieving Symptoms of Vaginal Dryness	

NOTE: If the IVR is expelled during the 7-day investigation period, the participant will be asked to rinse it using tap water and reinsert unless it is not appropriate to reinsert the expelled ring (e.g., lost in toilet, soiled). If participant is unable or unwilling to reinsert the expelled ring, she will be asked to store it, if possible, in a provided re-sealable bag and bring it to her next clinic visit. If she is unable or unwilling to reinsert the expelled ring, she will be asked to insert a new ring. Participants will be instructed to document this event in the daily diary.

Visit 2/5 - Second Ring Insertion

1. Participants will return to the clinic on day 7/56 (\pm 2 days) and submit completed daily diaries.
2. Participants will be asked to report any Adverse Events (AEs), whether or not they feel they were related to use of the investigational device. AEs will be recorded on the Adverse Event Form (Attached).
3. Participants will be asked to complete a Pre-Procedure Survey.
4. Participants will undergo a brief vaginal health assessment that will include a pH test and assessment of Vaginal Health Index (VHI) (see Table 6).
5. Participants will be instructed to remove the ring per the instructions for use and without clinician input, and will be asked to complete a post-removal survey. The survey will include a comments section for users to provide feedback on the instructions for use and any steps that were difficult to understand.
6. Participants will be asked to insert a new ring per the instructions for use and without clinician input, and to complete a post-insertion survey.
7. This ring (VR101 or sham control), followed by a third and fourth device will be used consecutively, each to remain in the vagina for 7 ± 2 days.

Visit 3/6 – Final Crossover Arm Ring Removal

1. Participants will return to the clinic on day 28/77 (\pm 2 days) and submit completed daily diaries.
2. Participants will be asked to report any Adverse Events (AEs), whether or not they feel they were related to use of the investigational device. AEs will be recorded on the Adverse Event Form (Attached).
3. Participants will be asked to complete a Pre-Procedure Survey.
4. Participants will undergo a brief vaginal health assessment that will include a pH test and assessment of Vaginal Health Index (VHI) (see Table 6).
5. Participants will be instructed to remove the ring per the instructions for use and without clinician input, and will be asked to complete a post-removal survey.
6. Participants will be asked provide a urine sample for a pregnancy test.
7. Participants will be asked to complete an End-of-Use survey.

J3 Bioscience, Inc.	Clinical Investigation Plan and Protocol CI02	CI02-CIP Rev. 08 Page 40 of 75
	A Pivotal Clinical Investigation to Evaluate the Safety and Efficacy of J3 Bioscience Lubricating Intravaginal Ring VR101 in Relieving Symptoms of Vaginal Dryness	

8. During Visit 6, the Participant will be given a package containing the Participant Number followed by the letter “C” (for example Participant 1 will be given a package labeled “1C”) regardless of her randomization status. This package will contain 12 each VR101 devices (one for each week and 3 spares) and will be instructed to insert a new ring, again per the instructions for use and without clinician input.
9. Participants will be asked to complete a Post-Insertion survey.
10. During Visits 3 and 6, participants will be asked to return any additional unused devices (spares) left over from the previous package.
11. Devices administered will be used consecutively, each to remain in the vagina for 7 ± 2 days.

Final Visit (can be used for Participants who withdraw from the study between scheduled Visits)

1. When the crossover study blind is broken, V1S2 participants still using VR101 will be contacted and asked to discontinue VR101 use. A visit will be scheduled for the participant to return study products and disclose any Adverse Events or concomitant medication changes.
2. During the Visit, participants will be asked to provide a urine sample for a pregnancy test.

Visit 7 (all)/Visit 8 (V1S2 only) - Long-Term Safety Visit

1. Participants still enrolled in the study will return to the clinic on day 105/140 (± 2 days).
2. Participants will be asked to report any Adverse Events (AEs), whether or not they feel they were related to use of the investigational device. AEs will be recorded on the Adverse Event Form (Attached).
3. Participants will be asked to complete a Pre-Procedure Survey.
4. Participants will undergo a brief vaginal health assessment that will include a pH test and assessment of Vaginal Health Index (VHI) (see Table 6).
5. Participants will be instructed to remove the ring per the instructions for use and without clinician input, and will be asked to complete a post-removal survey.
6. Participants will be asked to provide a urine sample for a pregnancy test.
7. Participants will be asked to insert a new ring per the instructions for use and without clinician input, and to complete a post-insertion survey.
8. This device and 3 additional VR101 devices will be used consecutively, each to remain in the vagina for 7 ± 2 days.
9. During Visit 8, V1S2 participants will be given 4 additional VR101 devices

J3 Bioscience, Inc.	Clinical Investigation Plan and Protocol CI02	CI02-CIP Rev. 08 Page 41 of 75
	A Pivotal Clinical Investigation to Evaluate the Safety and Efficacy of J3 Bioscience Lubricating Intravaginal Ring VR101 in Relieving Symptoms of Vaginal Dryness	

Visit 8 (S1V2) or Visit 9 (V1S2) - Final Long-Term Safety Visit

1. Participants will return to the clinic on day 140 (S1V2) or day 168 (V1S2) (\pm 2 days).
2. Participants will be asked to report any Adverse Events (AEs), whether or not they feel they were related to use of the investigational device. AEs will be recorded on the Adverse Event Form (Attached).
3. Participants will be asked to complete a Pre-Procedure Survey.
4. Participants will undergo a brief vaginal health assessment that will include a pH test and assessment of Vaginal Health Index (VHI) (see Table 6).
5. Participants will be instructed to remove the ring per the instructions for use and without clinician input, and will be asked to complete a post-removal survey.
6. Participants will be asked to provide a urine sample for a pregnancy test.
7. Participants will be asked to complete an End-of-Use survey.
8. Participants will be asked to return all unused rings to the clinic.

5.4.4 Assessment of Vaginal Health Index (VHI)

The following instructions will be provided to clinical personnel:

- Insert speculum and open the blades sufficiently to expose the cervical os. Secure the position of the speculum.
- Complete Vaginal Health Index Assessment Form (see Table 5 below for VHI scoring) for the appropriate visit number and study participant ID.
- Sample vaginal fluid for pH measurement (exact method to be documented in the CI02 clinical protocol).
- Remove speculum.
- Ensure that all required fields on the VHI Score form are completely filled-in.

J3 Bioscience, Inc.	Clinical Investigation Plan and Protocol CI02	CI02-CIP Rev. 08 Page 42 of 75
	A Pivotal Clinical Investigation to Evaluate the Safety and Efficacy of J3 Bioscience Lubricating Intravaginal Ring VR101 in Relieving Symptoms of Vaginal Dryness	

Table 6. Scale for Scoring Individual Vaginal Health Index Components to arrive at a VHI Score

VHI Component	Vaginal Health Index Component Score				
	1	2	3	4	5
Elasticity	None	Poor	Fair	Good	Excellent
Fluid Volume	None	Scant amount (vault not entirely covered)	Superficial amount (vault entirely covered)	Moderate amount	Normal amount
Epithelial Integrity	Petechiae noted before contact	Bleeds with light contact	Bleeds with scraping	Not friable, thin epithelium	Normal
Moisture (Coating)	None Surface inflamed	None Surface not inflamed	Minimal	Moderate	Normal
pH	6.1 or above	5.6-6.0	5.1-5.5	4.7-5.0	4.6 or below

All Vaginal Health Component scores are determined by clinicians receiving the same training in the assessment and scoring of VHI components. VHI component scores shall be assessed according to the following metrics (Bachmann 1991):

Elasticity – Elasticity of the tissue as determined by the resistance of stretch noted with digital palpation

Fluid Volume – The quantity of secretions pooled in the posterior vaginal vault

Epithelial Integrity – Epithelial integrity as determined by color, rugation and friability of the vaginal surface with speculum insertion

Moisture – The appearance and spread of the secretions coating the vaginal vault

5.4.5 Participant Assessment of Vaginal Dryness Relief (Endpoint 2 and Exploratory Endpoints)

The following 4 questions will be asked at each clinical visit as part of each Pre-Procedure Survey. These questions will also be asked during each follow-up call.

1. *Think about the last 7 days. In how many of those days did you experience any vaginal dryness? ("Vaginal Dryness Frequency")*
2. *On average, how would you rate your vaginal dryness in the last 7 days? ("Weekly-Averaged Severity of Vaginal Dryness")*

J3 Bioscience, Inc.	Clinical Investigation Plan and Protocol CI02	CI02-CIP Rev. 08 Page 43 of 75
	A Pivotal Clinical Investigation to Evaluate the Safety and Efficacy of J3 Bioscience Lubricating Intravaginal Ring VR101 in Relieving Symptoms of Vaginal Dryness	

3. *On average, how would you rate your worst day of vaginal dryness symptoms? ("Peak Severity of Vaginal Dryness")*
4. *How would you rate your vaginal dryness in the last 24 hours? ("24-hour vaginal dryness severity")*

Possible responses for question 1 are integers from 0 to 7 (assuming the ring was in place for exactly 7 days), while possible responses for questions 2-4 are as follows:

"I have not experienced vaginal dryness"	(assigned a score of 0)
"Mild"	(assigned a score of 1)
"Moderate"	(assigned a score of 2)
"Severe"	(assigned a score of 3)

Responses to Question 2 prior to ring insertion and to Question 4 following use of the first VR101 for 7 days will be used to assess the validity of Claim 1.

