Participating women also were asked to report the frequency of their vaginal dryness symptoms throughout the study. They initially reported experiencing dryness an average of 4 days out of the prior 7 days. Once participants started using VR101, the reported frequency of vaginal dryness symptoms decreased to an average of 1.3 days during the first 7 days of ring use, 0.4 days during the second 7 days of ring use and remained lower than baseline 7 days after discontinuing ring use (1.8 days out of 7 days after VR101 use had been discontinued) (all $p < 0.005$, one-tailed, normally approximated Wilcoxon signed-rank test). While 20 of 21 women reported experiencing dryness symptoms in the 7 days prior to entering the study, only 7 of 21 and 4 of 21 reported experiencing any symptoms of vaginal dryness during the first and second week of VR101 use, respectively.

J3 Bioscience, Inc.	Clinical Investigation Plan and Protocol CI02	CI02-CIP Rev. 08 Page 17 of 75
	A Pivotal Clinical Investigation to Evaluate the Safety and Efficacy of J3 Bioscience Lubricating Intravaginal Ring VR101 in Relieving Symptoms of Vaginal Dryness	

Regarding safety, no serious safety concerns or adverse events were noted or reported by the participants or clinical study staff. Participants were asked if they experienced any unusual vaginal discomfort or discharge over the course of the investigation. There were 11 reports (out of 63 total surveys) of vaginal discomfort recorded and six reports (out of 63 total surveys) of vaginal discharge. It is important to note that for both vaginal discomfort and discharge reported, all participants but one rated discomfort and discharge with the lowest intensity score possible, “minimal/minor,” and that none of the participants consistently reported unusual discomfort or discharge throughout the study. Moreover, all 21 participants that enrolled successfully completed the study, including follow-up.

In total, these results demonstrate that VR101 shows promise for safely moisturizing and lubricating the vagina and supplementing the body’s natural lubrication in peri- and post-menopausal women experiencing symptoms of vaginal dryness. A complete summary of data from the pilot investigation CI01 can be found in Clinical Investigation CI01 Final Report which is included as an attachment to the Investigator’s Brochure.

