4.2.3 Hypotheses for Claims and Usability Testing

If both the primary efficacy and safety hypotheses are met, then hypotheses for Claims 1, 2, and 3 will be tested using a hierarchical testing approach in order to control for multiplicity. Claim 1 will be tested first and if the null hypothesis is rejected, then Claim 2 will be tested. If the null hypothesis for Claim 2 is rejected, then Claim 3 will be tested. Refer to Appendix B for survey questions used to assess the validity of the following claims.

Claim 1: VR101 relieves vaginal dryness symptoms for up to 7 days in a majority of participants, as assessed by users.

Vaginal dryness severity will be assessed throughout the study using participant's ranked responses to questions in a questionnaire (see Section 5.4.5 below). Severity will be scored on a 0 to 3 scale (3 being the worst possible rating). At each visit, participants will be asked to rate their vaginal dryness over the last 24 hours and the last 7 days. **Claim 1 will be validated if the**

J3 Bioscience, Inc.	Clinical Investigation Plan and Protocol CI02	CI02-CIP Rev. 08 Page 25 of 75
	A Pivotal Clinical Investigation to Evaluate the Safety and Efficacy of J3 Bioscience Lubricating Intravaginal Ring VR101 in Relieving Symptoms of Vaginal Dryness	

p-value associated with a two-tailed Student's t-test of the mean of the paired values between the *daily* vaginal dryness severity score reported on day 7 (survey question, Visit 2) and average *weekly* vaginal dryness severity score reported over the week prior to VR101 use (survey question, Visit 1 for study group V1S2, Visit 4 for study group S1V2) is less than 0.05. If the paired differences are observed not to be normally distributed, an appropriate non-parametric test will be substituted for the two-tailed Student's t-test. Additionally, a two-tailed 95% confidence interval of the paired dryness values will be reported.

Claim 2: VR101 is easy to use by following the provided instructions for use.

Null and Alternative Hypotheses for Claim 2:

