5.1.1 Study Endpoints

Used to Test Primary Efficacy Hypothesis:

1. $\Delta VHI_{VR101}(\text{day 28}) - \Delta VHI_{\text{sham}}(\text{day 28})$, the paired difference in vaginal dryness relief between VR101 and the sham control at day 28.

J3 Bioscience, Inc.	Clinical Investigation Plan and Protocol CI02	CI02-CIP Rev. 08 Page 27 of 75
	A Pivotal Clinical Investigation to Evaluate the Safety and Efficacy of J3 Bioscience Lubricating Intravaginal Ring VR101 in Relieving Symptoms of Vaginal Dryness	

Used for Validation of Claim 1:

2. The paired difference between self-reported 24-hour vaginal dryness severity reported after the first 7 days of VR101 use (see Section 5.4.5, collected at Visit 2 or 5 depending on study group) and weekly-averaged vaginal dryness severity prior to ring use (also see Section 5.4.5, collected at Visit 1 or Visit 4 depending on study group).

Used for Validation of Claim 2:

3. Participant reported ease of use of VR101 (measured on a scale of -4 to 4, see Section 5.4.6).

Used for Validation of Claim 3:

4. Self-reported perception that VR101 was comfortable during use, measured on a scale of -4 to 4 (see Section 5.4.6).

Used to Test Primary Safety Hypothesis:

5. The proportion of Serious Adverse Device Effects (SADE) in relation to the total number of VR101 devices use in the study.

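### Claim 1 compares a 7-day-average dryness rating before VR101 with a last-24-hours rating on VR101, so reported dryness can appear to fall without any change in symptoms; the size depends on how women answer the weekly item.

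*Combined protocol and SAP*

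**What the plan says.** Section 5.4.5 lists the two items. Question 2 asks "how would you rate your vaginal dryness in the last 7 days", as an average. Question 4 asks "How would you rate your vaginal dryness in the last 24 hours". Both are scored 0 to 3, and 0 means that no vaginal dryness was experienced. The same section assigns them to Claim 1: "Responses to Question 2 prior to ring insertion and to Question 4 following use of the first VR101 for 7 days". Endpoint 2 in 5.1.1 is defined in the same way, as "The paired difference between self-reported 24-hour vaginal dryness severity reported after the first 7 days of VR101 use" and the weekly-averaged severity before ring use. Section 4.2.3 and Appendix B agree.

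Section 4.2.3 tests the mean paired difference with a two-sided t-test at 0.05, or a non-parametric test if the differences are not normal. There is no sham term. It also states: "At each visit, participants will be asked to rate their vaginal dryness over the last 24 hours and the last 7 days".

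Section 5.4.3 adds: "Participants will be instructed to refrain from vaginal intercourse 24 hours prior to each scheduled visit". A woman who reports intercourse in that period is rescheduled where this can be done.

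Claim 1 is tested only after the primary efficacy and safety hypotheses are met, and it must succeed before Claim 2, and then Claim 3, is tested (4.2.3, 8.11). Section 8.5 says the claims tests do not bear on whether the investigation succeeds. No section explains the mixed windows; 6.4 explains only why participant-reported endpoints were chosen.

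**The concern.** A paired test against zero assumes that both readings would have the same mean if symptoms did not change. Two features of the plan can break that assumption, and both push toward apparent benefit.

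- **Response options.** A woman with any dry day in the week cannot literally choose 0 on Question 2. She chooses 0 on Question 4 whenever the last day was symptom-free.
- **Intercourse.** The 24-hour request covers all of the Question 4 window but about one of the seven days in the Question 2 window. Qualifying dryness may be dryness that interferes with intercourse (5.3.1), and severity is graded by interference with activities (Appendix B). One possible source of higher ratings is thus mostly kept in the baseline and removed from the follow-up.

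At stake are the 7-day relief statement on the label and access to the tests of Claims 2 and 3. Section 4.1.3 relies on Claim 2 to justify over-the-counter use.

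**Working it through.** **Inputs from the documents.** n = 60 completers (8.2); two-sided alpha 0.05 (8.1); pilot baseline, where "They initially reported experiencing dryness an average of 4 days out of the prior 7 days" and 20 of 21 women had dryness in that week (2.4). The plan gives no effect size, SD or power for Claim 1.

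**Check of the power function.** The plan's only comparable figure is 88% for the VHI endpoint (difference 0.89, SD 2.14). The noncentrality is 0.89 / (2.14/√60) = 3.22. Power is 88.7% from the noncentral t distribution, and Φ(3.22 − 1.96) = 89.6% from the normal approximation. The plan's figure is reproduced.

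**Shift under four ways of answering Question 2, with no effect on reported dryness.** Let p = 4/7 be the mean share of dry days and m the mean severity on dry days (m is assumed).

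1. *True mean of the seven days.* The expected weekly score is p·m, and so is the expected 24-hour score. The shift is 0.
2. *Mean rounded to the nearest category.* The shift is rounding error only, 0.01 to 0.08 points.
3. *Rounded mean, but at least mild after any dry day.* The shift is 0.10 to 0.42 points downward. As a hand check with all dry days mild, the weekly mean is 20/21 = 0.95 and the 24-hour mean is 4/7 = 0.57, a fall of 0.38. If the two readings are independent, the SD of differences is √(0.95×0.05 + 0.57×0.43) ≈ 0.54, so t ≈ −0.38 / (0.54/√60) ≈ −5.5.
4. *Severity on dry days.* The expected shift is about −(1 − p)·m = −(3/7)m. With m = 1 this is −0.43; with 30/50/20% mild/moderate/severe, m = 1.9 and it is −0.81. Simulated shifts run from 0.39 to 0.89 points downward.

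**Rate of favourable false validation** (day-level simulation, n = 60, 1,500 trials per scenario; mean dry-day share 4/7; severity mixes from all mild to 20/50/30% mild/moderate/severe; intercourse not modelled):

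| How Question 2 is answered | p < 0.05 with a fall |
|---|---|
| True 7-day mean | about 2-3% |
| Rounded, no minimum | 2-15%, highest when every dry day is mild |
| Rounded, at least mild after any dry day | 9-100%, highest when every dry day is mild |
| Severity on dry days | about 100% |
| Same item at both times | 2-3% |

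**Adding the intercourse request to the true-mean case.** If a day with intercourse raises severity by up to one level and a share π of other days has intercourse, the shift is at most (6/7)π: 0.12 for π = 1/7 and 0.24 for π = 2/7. The simulation gives 0.11 and 0.22, with false validation of 11% and 34%. Both π and the one-level rise are assumptions.

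**Sensitivity to a given artefact.** With an SD of differences of 1.0 (assumed), a spurious shift of 0.1, 0.2, 0.3 or 0.5 points gives a significant result in 12%, 33%, 63% or 97% of trials. With an SD of 0.8 the figures are 16%, 48%, 82% and 100%; with 1.2 they are 10%, 25%, 48% and 89%.

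**The case against.** A reader might infer that Claim 1 is almost certain to be validated falsely. The documents do not support that, for three reasons.

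- **The gate.** Claim 1 is reached only if VR101 beats sham on VHI and the safety criterion is met. If the ring did nothing at all, the efficacy test would open that gate in about 2.5% of trials. The rates above therefore describe the case where the gate has passed, with VR101 improving VHI but not reported dryness.
- **The weekly item asks for an average.** No scoring rule forces at least mild after one dry day. If women report a true mean and intercourse does not matter, there is no bias.
- **The 4-in-7 figure is borrowed.** It comes from 21 pilot women, some with a baseline VHI of 23 or more (8.2), whom this trial excludes. Dry-day frequency in this trial is not given.

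These points stand, and they limit the size of the problem. It would also be too strong to call abstention mandatory: it is an instruction, with rescheduling only where feasible, and it applies before baseline visits too.

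A day-specific follow-up also suits a claim of relief lasting to day 7. That is correct, but it defends only the follow-up item. It gives no reason to choose a 7-day average as the baseline. Nor is the no-bias case a safe default, because the form offers four whole-number options: a woman with four mild dry days averages 4/7 = 0.57 and must choose between mild and a statement that she had no dryness.

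**Conclusion.** The mismatch is certain, because four places in the plan state it consistently. Its direction, where there is any bias, favours the claim. Its size is not fixed by the documents: favourable false validation runs from nominal (about 2-3%) to about 100%, depending mainly on how women read the weekly item and partly on whether intercourse affects the rating. All figures assume 60 women, the pilot's dry-day frequency, the stated severity mixes, and that the VHI and safety gates have passed.

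A reader might also infer that the trial's overall result is compromised. It is not: 8.5 keeps the claims out of the success criteria, and the primary VHI comparison does not use these items. The damage is confined to the 7-day relief claim and the gate to Claims 2 and 3. This should be fixed, but it is not a fatal defect.

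**What to change.** Before the blind is broken:

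- In 4.2.3, Endpoint 2 of 5.1.1, 5.4.5, 8.12 and Appendix B, set the Claim 1 baseline to the 24-hour rating taken just before the first VR101 insertion (Visit 1 for V1S2, Visit 4 for S1V2). Keep the 24-hour rating at Visit 2 or 5 as the follow-up. The intercourse request then applies equally to both readings.
- Report the 7-day versus 7-day change as a supportive analysis.
- First confirm that the Visit 1 form carries the 24-hour item. Section 4.2.3 and Appendix B say it is asked at each visit, but 5.4.5 places it in the Pre-Procedure Survey, and Visit 1 uses a Pre-Study Survey (5.4.3). If it was not collected, use the 7-day item at both times.
- State that matching the windows does not remove placebo response or regression to the mean, because Claim 1 remains a before-after test. The change over the sham period is already collected and can be reported alongside.

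The cost is a mid-study amendment needing sponsor and IRB approval (section 10). If the Visit 1 item exists, no new data are needed. A single-day baseline is noisier, and some women will score 0 at baseline, so the apparent effect may be smaller.
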